## **7.3 Previous Treatment and Concomitant Medications**

Number of prior and concomitant medications per subject, and by generic name will be summarized.

A prior medication is defined as any medication taken at the time of entry into Study 1311.2 and prior to the first dose of risankizumab. A concomitant medication is

defined as any medication that started prior to the first dose of risankizumab in Study 1311.2 or Study 1311.13 and continued to be taken after the first dose of risankizumab or any medication that started after the first dose of risankizumab, but not after the last dose of risankizumab + 21 days. The number and percentage of subjects who had taken medications will be summarized by generic drug name assigned by the World Health Organization (WHO) for both prior and concomitant medications.

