3. DESCRIPTION OF DESIGN AND TRIAL POPULATION

3.1 OVERALL TRIAL DESIGN AND PLAN

This open label extension trial (OLE), investigates the additional safety and efficacy of the 90 mg dose of BI 655066. Approximately 100 patients who meet the entry criteria are planned for inclusion in this trial, rolling over from the preceding 1311.2 trial. The treatment will be open label.

The treatment period will be approximately four years of administration starting with first administration of BI 655066 in either trial 1311.2 or 1311.13, followed by a 12 week follow up period. After 01-May-2018 and approval of this protocol amendment in each respective country, the next study visit will be the Extended EOS visit and therewith the last visit in this study. Patients who have completed the study without early treatment discontinuation will be offered to roll over to M15-997 open label extension (OLE) trial if they fulfill the in- and exclusion criteria for the M15-997 trial. Refer to [section 6.2.3](#).

Patients rolling over from the preceding trial 1311.2 will have to complete the treatment period in that trial, or complete the entire trial including the follow up period, reaching end of study. If, during the follow up period of the preceding trial (at any visit from week 24 and onwards in trial 1311.2) loss of response is detected, the patient can roll over in this extension trial. For this, loss of response is defined as $< \text{PASI}_{50}$.

Extended visit 1 of this trial should preferably be performed as a combined visit the same day as End of Study visit of 1311.2, or within an interim period of maximum 6 weeks thereafter.

1311.2

[figure not shown]
[figure not shown]

Figure 3.1:1 Guideline for roll over of patients from 1311.2 to OLE study 1311.13

After the approval of this protocol amendment in each respective country, all patients will follow [Flow Chart](#) (Extended Dosing Period) and receive 90mg BI 655066 subcutaneously at their Extended visit 1 (EV1). From EV1 onwards, BI655066 will be administered subcutaneously every 12 weeks during the trial. At EV2, if there is a lack of response, defined as <PASI90, the dose should be increased to 180mg for the remainder of the trial (see Fig 3.1.2).

For ongoing patients under the previous protocol amendment (Pre-Extended Dosing Period, [see Fig 3.1.3](#)), EV1 should be conducted at the following time points:

1. For ongoing patients with ≥ 12 weeks since the EOT visit: Conduct EV1 as soon as possible

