4.2.2 Restrictions

4.2.2.1 Restrictions regarding concomitant treatment

The medications (or classes of medication) listed in [Table 4.2.2.1:1](#) must not be taken for the specified times before the roll-over visit and for the whole duration of the study including the Extended Follow-up Period.

Table 4.2.2.1: 1 Restricted medications

Investigational products not otherwise described below (except 1311.2 study drug)	Throughout the duration of preceding trial 1311.2, and for the whole duration of this trial, including any interim period between the trials and the Extended Follow-up Period.
Any biological agents, including but not limited to infliximab, etanercept, adalimumab	Throughout the duration of preceding trial 1311.2, and for the whole duration of this trial, including any interim period between the trials and the Extended Follow-up Period
Oral or injectable psoriasis medications (not biologicals) including but not limited to retinoids, methotrexate, cyclosporine, fumarates, or any other drugs known to possibly benefit psoriasis. Systemic corticosteroids in any dosage form. Any drug known to interfere with or to aggravate psoriasis including but not limited to lithium and interferons, or Phototherapy (UVB, PUVA, UVA).	Throughout the duration of preceding trial 1311.2, and for the whole duration of this trial, including any interim period between the trials and the Extended Follow-up Period
Steroids, retinoids, vitamin D analogs, vitamin A analogs and anthralin in any formulation (i.v., s.c., topicals, oral).	Throughout the duration of preceding trial 1311.2, and for the whole duration of this trial, including any interim period between the trials and the Extended Follow-up Period. (for exceptions cf. Section 4.2.1)

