5.2.2.2 Adverse event and serious adverse event reporting

All adverse events, serious and non-serious, occurring during the course of the clinical trial (i.e., from signing the informed consent onwards through the Residual Effect Period (REP) /Extended follow-up period) will be collected, documented and reported to the sponsor by the investigator on the appropriate CRF(s) / eCRFs / SAE reporting forms. Reporting will be done according to the specific definitions and instructions detailed in the ‘Adverse Event Reporting’ section of the Investigator Site File.

Reporting of Adverse Events in Remote Data Capture system (RDC):

AEs that are ongoing at the end of the previous trial (1311.2) will have to be re-entered, and any adverse events that have started between the two trials (in the event that the 6 weeks time-window is used), will also be entered into the 1311.13 RDC system.

Reporting of Adverse Events on the SAE form:

Specific instructions for the SAE reporting process concerning SAE forms in previous and roll-over studies will be provided in the ISF.

The REP for BI 655066 is 12 weeks. Therefore, all events reported within 12 weeks of the last trial medication will be considered on treatment. All adverse events will be reported up until the last per protocol visit (Extended EOS visit), which is 84 (+7 days) days after the last dose of trial medication.

The investigator does not need to actively monitor patients for AEs once the clinical trial has ended. However, if the investigator becomes aware of an SAE(s) that occurred after the patient has completed the clinical trial (including any protocol required REP and / or follow-up), it should be reported by the investigator to the sponsor if considered relevant by the investigator.

For each adverse event, the investigator will provide the onset date, end date, intensity, treatment required, outcome, seriousness, and action taken with the investigational drug. The

Proprietary confidential information.

© 2018 Boehringer Ingelheim International GmbH or one or more of its affiliated companies. All rights reserved.

This document may not - in full or in part - be passed on, reproduced, published or otherwise used without prior written permission.

investigator will determine the relationship of the investigational drug to all AEs as defined in [Section 5.2.2.1](#).

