7.4 HANDLING OF MISSING DATA

Use of inappropriate concomitant medication to treat psoriasis will be considered as failure when deriving response variables, e.g. PASI₉₀.

Further details on the handling of missing data will be provided in the Trial Statistical Analysis Plan.

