### **Definition of Final Observation (Applicable to Safety Analyses)**

Final observation in the entire study is defined as the last non-missing observation collected within 105 days after the last dose of risakizumab.

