### **11.2 Analysis of Adverse Events**

#### **11.2.1 Treatment Emergent Adverse Events**

Treatment emergent adverse events (TEAEs) are defined as any event with an onset that is after the first dose of risankizumab in this study and with an onset date within 105 days after the last dose of study drug in the analysis period.

Events where the onset date is the same as the study drug start date are assumed to be treatment emergent, unless the adverse event start time is prior to the study drug start time. If an incomplete onset date is collected for an adverse event, the event will be assumed to be treatment-emergent unless there is other evidence that confirms that the event is not treatment-emergent (e.g., the event end date is prior to the study drug start date).

The number and percentage of subjects experiencing treatment-emergent TEAEs will be tabulated using the Medical Dictionary for Drug Regulatory Activities (MedDRA®) system organ class and preferred term.

Considering the fact that some subjects had dose escalation due to lack of efficacy at EV2, selected safety tables will be generated breaking down by the group of subjects who remained at 90 mg throughout the study, the group of subjects who received 180 mg at EV2, and total.

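### SAP 7.3 stops counting newly started medication 21 days after the last dose, so the concomitant-medication summary omits new drugs from day 22 to Extended EOS

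*SAP*

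**What the plan says.** SAP 7.3 has two routes to concomitant status. A drug qualifies if it was already in use at the first risankizumab dose and continued, or if it started later, "but not after the last dose of risankizumab + 21 days". No reason is given for 21 days.

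The other time limits in the documents are these:

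- **Dosing interval.** Protocol 3.1: "BI655066 will be administered subcutaneously every 12 weeks during the trial".
- **Residual effect period.** Protocol 5.2.2.2: "The REP for BI 655066 is 12 weeks".
- **Last visit and end of AE collection.** The same section places Extended EOS at a time "which is 84 (+7 days) days after the last dose of trial medication".
- **Exposure.** SAP 9.0 adds 84 days to the interval from first to last dose.
- **Treatment-emergent events.** SAP 11.2.1 takes events "with an onset date within 105 days after the last dose of study drug in the analysis period".
- **Final safety observation.** SAP 6.0 takes values "collected within 105 days after the last dose of risakizumab".
- **Restricted medication.** Protocol 4.2.2.1 bars the listed drugs "for the whole duration of the study including the Extended Follow-up Period".

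Two protocol rules say what restricted medication does to efficacy data. Protocol 7.4: "Use of inappropriate concomitant medication to treat psoriasis will be considered as failure when deriving response variables". Protocol 3.3.4.1 instead drops efficacy and PD data assessed after such use. SAP 10.1 specifies observed cases without imputation and has no rule for prohibited medication.

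**The concern.** The SAP treats a patient 60 days after the last dose as still exposed and still at risk of treatment-emergent events. A drug started on that day is nevertheless not concomitant. New psoriasis treatment is plausible after dosing stops, particularly in a patient who stopped early, and that is the period the definition leaves out.

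Two things are at stake. The certain one is an incomplete descriptive table: a reader comparing late adverse events or the final PASI with the medication summary would not see drugs begun in most of the follow-up. The conditional one concerns response. SAP 7.3 contains the only definition of concomitant medication in the SAP, and both the deviation category in SAP 7.4 and the failure rule in Protocol 7.4 use that word. A programmer could carry the 21-day limit into either, and nothing in the SAP says not to.

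**Working it through.** The plan gives no derivation of 21 days. The nearest figure is in the SAP's section on events per 100 patient-years, which describes 105 days as five half-lives: 105 / 5 = 21. The cut-off therefore equals one half-life on the SAP's own basis, while the safety windows use five. That this is where 21 comes from is an inference.

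**Share of the post-dose period outside the window**

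Inputs: cut-off 21 days (SAP 7.3); follow-up 12 × 7 = 84 days (Protocol 5.2.2.2); visit allowance +7 days (same section); TEAE limit 105 days (SAP 11.2.1). For an early discontinuer, the Extended EOT takes place at the latest at the next scheduled visit, and EOS follows 12 weeks later (Protocol 6.2.3). No dose is given at that early EOT (Flow Chart, footnote 10). EOS can then fall 84 + 84 = 168 days after the last dose.

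Formula: uncovered days = end of period − 21; share = uncovered days / end of period.

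| Period ends at | Uncovered days | Share |
|---|---|---|
| EOS, day 84 | 84 − 21 = 63 | 75.0% |
| EOS with +7, day 91 | 91 − 21 = 70 | 76.9% |
| TEAE limit, day 105 | 105 − 21 = 84 | 80.0% |
| Early discontinuer, EOS at day 168 | 168 − 21 = 147 | 87.5% |

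The first row applies to patients who finish on schedule. Under Protocol 3.1, the next visit after 01-May-2018 and local approval of the amendment is the Extended EOS, so an ongoing patient closing out also has about 63 uncovered days before the last PASI.

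The 80% row compares two rules. It is not a share of observed time, because for a completer AE collection ends at 84 (+7) days.

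**Would a 105-day limit close the gap?** It would for a completer. For the early discontinuer, 168 − 105 = 63 days would remain uncovered.

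**Does the gap reach Week 48?** SAP Table 1 gives Week K a target day of K × 7 + 1 and an interval from K × 7 − 40 to K × 7 + 43. For K = 48 the target is day 337 and the interval is days 296 to 379. The cases below take the first dose in this study to be at Extended Visit 1.

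- Dosed at Week 48 or later: the cut-off is day 337 + 21 = 358 or later. Every drug started before a Week 48 PASI on day 337 is inside the window.
- Last dose at Week 36 (day 253), EOT at day 337: the cut-off is 253 + 21 = 274, which is 337 − 274 = 63 days before that PASI.
- Last dose at Week 24 (day 169), EOT at Week 36, EOS near day 337: the cut-off is 169 + 21 = 190, which is 337 − 190 = 147 days before that PASI.

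The last two patients enter the Week 48 analysis because SAP 10.1 uses all observed values and does not remove PASI recorded after dosing has stopped.

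**The case against.** The case for leaving this alone is substantial, and much of it stands.

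A reader might infer that prohibited psoriasis treatment in follow-up goes uncounted. The documents do not support that. Protocol 4.2.1 requires all concomitant and rescue therapy to be recorded in the eCRF. The Flow Chart schedules concomitant therapy into follow-up. SAP 7.4 counts patients who received excluded or prohibited medication and states no day limit. For the same reason it would be wrong to say that late adverse events have no medication record. In addition, drugs begun earlier and continued, or begun by day 21, remain in the summary.

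A reader might also infer that late response is overstated. As written, the SAP has no mechanism for that. SAP 7.3 feeds counts by generic name. SAP 10.1 has no failure flag, so replacing 21 with a larger number would by itself change no PASI or sPGA result. No adverse-event analysis uses concomitant medication either. The larger efficacy problem is that Protocol 7.4 and Protocol 3.3.4.1 disagree and SAP 10.1 implements neither.

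The uncovered period is also short against the whole trial. Treatment lasts about four years, roughly 4 × 365 = 1,460 days, and 63 / 1,460 is about 4%.

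What this does not answer is the mismatch itself. A stated rule removes new drugs from a planned table over most of follow-up, for patients who complete as well as those who stop. The absence of a day limit in SAP 7.4 helps only if nobody reads the SAP's sole definition of the term into it.

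**Conclusion.** The inconsistency is real and limited in reach. The concomitant-medication summary omits drugs newly started from day 22 to Extended EOS: 63 of 84 days for a completer on schedule, and up to about 147 of 168 days for an early discontinuer whose EOT is held at the next planned visit. The second figure ignores visit allowances.

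Any effect on Week 48 response needs two conditions together: the patient stopped dosing before Week 48, and the 21-day definition is applied to the failure rule in Protocol 7.4. The documents do not state that link, so bias in response is a possibility to close off and not an established result. They also do not say how many patients start new medication in this interval, so the number affected cannot be estimated.

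The trial is descriptive with no statistical testing, which limits the consequence to what the tables show. It is still worth correcting before database lock.

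**What to change.** 1. In SAP 7.3, end the window for newly started medication at the Extended EOS visit. Do not use 105 days, which leaves up to 63 days uncovered for early discontinuers and, if carried into SAP 7.4, would restrict a count that now has no limit.
2. State that the deviation count in SAP 7.4 and the failure rule in Protocol 7.4 cover use up to Extended EOS and are not subject to the 21-day limit.
3. In SAP 10.1, reconcile Protocol 7.4 (failure) with Protocol 3.3.4.1 (later data excluded) and write the chosen handling into the response derivation.

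Items 1 and 2 are a line or two and need no new data, since therapy is already recorded through EOS. Item 3 costs more: it is a new derivation rule, needs a decision between two conflicting protocol statements, and needs programming before lock.

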#### **7.4 Protocol Deviation**

Number and percentage of subjects who reported at least one of the following protocol deviation categories will be provided.

- Subject entered into the study even though she/he did not satisfy entry criteria
- Subject who developed withdrawal criteria during the study and was not withdrawn
- Subject who received wrong treatment or incorrect dose
- Subject who received excluded or prohibited concomitant

#### **8.0 Patient Disposition**

The number and percentage of subjects for each of the following categories will be summarized by investigator:

- Number of subjects treated
- Subjects completed
- Subjects who discontinued study drug (by reason)
- Subjects who discontinued study (by reason)

## **9.0 Study Drug Exposure and Compliance**

Study drug exposure (days) will be summarized using the sample size, mean, standard deviation, minimum, median and maximum. Study drug exposure will be summarized as follows:

### **Risankizumab Exposure (in Days):**

The Risankizumab Exposure (total duration during Study 1311.2 and this study) will be defined as follows:

The Risankizumab Exposure = Last risankizumab dose date – First risankizumab dose date (either in this study or Study 1311.2) + 84.

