2. RATIONALE, OBJECTIVES, AND BENEFIT - RISK ASSESSMENT

2.1 RATIONALE FOR PERFORMING THE TRIAL

The phase I, single rising dose study (1311.1) has shown proof of concept and proof of efficacy for BI 655066 in patients with moderate to severe psoriasis.

The preceding phase II study (1311.2) will allow for the evaluation of the efficacy, safety, tolerability, pharmacokinetics and pharmacodynamics of three different dose regimens (18 mg, 90 mg and 180 mg) of BI 655066, as well as dose-finding of BI 655066 for further studies. In addition the 1311.2 trial will compare the efficacy of BI 655066 with Stelara[®], an approved therapy for patients with moderate to severe psoriasis.

The data generated from this extension study is anticipated to provide additional safety data of up to approximately four years treatment in approximately 100 patients treated with BI 655066. Furthermore the study is being performed in order to allow extended access to a potential beneficial intervention, according to the principles laid down in the Declaration of Helsinki.

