#### 4. Adverse Event per 100 Patient-years of Exposure

Adverse events occurring during the entire study will be presented by event rate per 100 patient-year.

AEs per 100 patient-years of exposure is defined as the number of AEs divided by the total exposure in 100 patient-years. Note that one event per preferred term per day per subject will be counted in the calculation of the number of AEs (i.e., a preferred term will not be counted twice on the same day for the same subject). See the calculation method below.

$$100 \times \frac{\text{Number of TEAEs}}{\text{Total Patient Years}}$$

where total patient years is defined as the sum of the study drug exposure (defined as date of last dose – date of first dose + 105 days (5 half-lives)) of all subjects normalized by 365.25, and rounded to one decimal place.

The following summaries of AEs per 100 patient-years of exposure will be generated:

- Adverse event overview
- TEAE by SOC and PT
- SAE
- Treatment emergent adjudicated CV events
- Treatment emergent malignancies
- Serious treatment emergent malignancies

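### SAP 9.0 reports elapsed time since the first risankizumab dose as exposure, so planned intervals without dosing count as treatment

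*SAP*

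**What the plan says.** SAP 9.0 (Risankizumab Exposure) describes the quantity as "total duration during Study 1311.2 and this study" and computes it as "Last risankizumab dose date – First risankizumab dose date (either in this study or Study 1311.2) + 84". The Compliance paragraph that follows adds a count of subjects dosed at each administration visit and a summary of the cumulative number of doses.

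SAP 11.2.1 item 4 has a separate definition for AE rates per 100 patient-years: "date of last dose – date of first dose + 105 days (5 half-lives". It does not say in which study the first dose is meant. Treatment-emergent events are those with onset "after the first dose of risankizumab in this study and with an onset date within 105 days after the last dose of study drug". Protocol 5.2.2.2 sets a 12-week residual effect period, under which "all events reported within 12 weeks of the last trial medication will be considered on treatment".

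The design puts undosed time inside these spans in two places.

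- **Study 1311.2.** Protocol 3.1 separates the treatment period from the follow-up and places visits from week 24 onward in follow-up. Protocol 6.2.1 ends that trial at week 48. Protocol 3.1 allows up to 6 further weeks before EV1.
- **Pre-Extended Dosing Period of this study.** Protocol Figure 3.1:3 and SAP Figure 3 show EOT followed by visits out to EOT + 48 weeks. Protocol 3.1 then provides for restarting such patients: "For ongoing patients with ≥ 12 weeks since the EOT visit: Conduct EV1 as soon as possible".

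Protocol 2.1 presents the expected yield as "additional safety data of up to approximately four years treatment in approximately 100 patients treated with BI 655066".

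**The concern.** Last dose minus first dose plus one dosing interval equals time on treatment only if dosing is continuous. Here interruptions are planned. A table headed as risankizumab exposure would include follow-up during which no dose was scheduled.

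The primary objective in Protocol 2.2 is safety under long-term treatment, and there is no control arm. Duration of exposure is therefore one of the main figures by which a reader judges how much the safety data can show. Protocol 2.3 says that 75% of 1311.2 patients will have received BI 655066, so the first interval need not be confined to a few patients. The AE-rate denominator in SAP 11.2.1 has the same first-to-last form, so it needs checking too.

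**Working it through.** The documents give no exposure total, patient-years or AE rate, so there is no planned figure to reproduce. Only the tails can be checked: 12 × 7 = 84 days, and 105 / 5 = 21 days per half-life.

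**Formulas**

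- SAP 9.0: E = t(last) − t(first) + 84.
- Gap-adjusted: E* = Σ min(days to next dose, 84) over all doses but the last, + 84 for the last.
- Excess: E − E* = Σ max(0, interval between doses − 84).

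**1311.2 gap, patient on risankizumab who reaches week 48**

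From the documents: 12-weekly dosing from EV1 (Protocol 3.1), and EV1 at week 48 to 54. Assumed, because the 1311.2 dosing calendar is not given: last 1311.2 dose at week 0, 12 or 24, and 156 weeks from EV1 to the last dose. Then E = (48 + 156) × 7 + 84 = 1512 days, or (54 + 156) × 7 + 84 = 1554 days. The excess is (EV1 week − last dose week − 12) × 7.

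| Last 1311.2 dose | EV1 | E (days) | E* (days) | Excess | Share of E |
|---|---|---|---|---|---|
| week 24 | week 48 | 1512 | 1428 | 84 | 5.6% |
| week 24 | week 54 | 1554 | 1428 | 126 | 8.1% |
| week 12 | week 48 | 1512 | 1344 | 168 | 11.1% |
| week 12 | week 54 | 1554 | 1344 | 210 | 13.5% |
| week 0 | week 48 | 1512 | 1260 | 252 | 16.7% |
| week 0 | week 54 | 1554 | 1260 | 294 | 18.9% |

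The smallest share is not sensitive to the assumed duration. With 208 weeks from first to last dose it is 84 / (208 × 7 + 84) = 84 / 1540 = 5.5%. With 120 weeks of dosing after EV1 it is 84 / ((48 + 120) × 7 + 84) = 84 / 1260 = 6.7%. The 156 weeks is on the long side, since Amendment 3 (10 June 2015) to 1 May 2018 is 151 weeks. A shorter period raises every share.

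**Other patients**

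- Roll-over at week 24 for loss of response, EV1 at week 24: (24 − 0 − 12) × 7 = 84 days if last dosed at week 0, and none if last dosed at week 12 or 24.
- First risankizumab dose at EV1: none.
- Both gaps, illustrative outer case with doses at weeks 0, 54 and 66, then 12-weekly from week 114 to week 198: E = 198 × 7 + 84 = 1470; E* = 11 × 84 = 924; excess 546 days (37%).

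**AE rates, if the first dose in SAP 11.2.1 item 4 means the first in this study**

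Only patients dosed in the Pre-Extended period and restarted at EV1 are affected. Take EV1 at EOT + 12 to EOT + 48 weeks. The interval from the previous dose is 12 to 48 weeks if the patient was dosed at EOT, or 24 to 60 weeks if last dosed 12 weeks earlier. Less the 15-week (105-day) tail, this leaves 0 to 231 or 63 to 315 days. Assume 156 weeks from first to last in-study dose. The denominator is then 156 × 7 + 105 = 1197 days, and the uncovered share s runs from 0% to 315 / 1197 = 26.3%.

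Events in that interval are counted as well. If the event rate there is r times the on-drug rate, the reported rate differs from the on-drug rate by −s(1 − r). At s = 26.3% this is −26% for r = 0, −13% for r = 0.5, 0 for r = 1 and +13% for r = 1.5.

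**If the first dose were read as the 1311.2 dose**

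Treatment-emergent events still start in this study, so 24 to 54 weeks of denominator could hold no countable event. On 208 × 7 + 105 = 1561 days, that is 168 / 1561 = 10.8% to 378 / 1561 = 24.2%.

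**The case against.** Four arguments have weight.

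1. **SAP 9.0 says what it measures.** The phrase total duration mirrors the protocol's treatment period, which is counted from first administration in either trial, and the cumulative dose count shows actual dosing. This stands in part: the formula is sound as elapsed time. It does not justify the label of exposure, and a dose count gives neither exposure days nor a rate denominator.
2. **AE rates are not shown to be biased.** A reader might infer that they are diluted, or that off-drug events inflate them. The documents support neither. In-study gap events and gap time enter numerator and denominator together, and the sign depends on an off-drug rate that nobody has stated. A reader might also assume that patient-years start in 1311.2. Item 4 has its own inline definition, and both the Rx-day convention in SAP 6.0 and the treatment-emergent rule count from the first dose in this study. That is the likelier reading, though the text leaves it open.
3. **The protocol does not contradict the treatment-emergent rule on gaps.** A reader might take the 12-week period in Protocol 5.2.2.2 as excluding events in an earlier gap. It is anchored on the last trial medication, as is Protocol 7.3.3. The SAP limit, "with an onset date within 105 days after the last dose of study drug in the analysis period", has the same structure. The difference between them is 84 against 105 days, which is a separate matter.
4. **Undosed is not the same as drug-free.** The SAP allows 105 days for five half-lives, and Protocol 1.2 and 2.3 report single-dose effects lasting to week 24 or beyond. This stands, so the excess is best described as time outside the formula's own 84-day window.

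The trial is also descriptive, and its primary safety endpoints are tabulated as subject counts and percentages, which the SAP 9.0 formula does not enter. That limits the severity.

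**Conclusion.** The point holds for the exposure summary. As written, SAP 9.0 counts planned intervals without dosing as risankizumab exposure. A patient on risankizumab in 1311.2 who completed week 48 carries at least about 84 excess days, roughly 5% or more of the reported figure. This rests on a last 1311.2 dose no later than week 24, which the follow-up visits from week 24 suggest but the documents do not state. The higher shares in the table, and the 37% outer case, depend on assumed calendars and are per-patient illustrations. The study-wide size cannot be determined without the 1311.2 dosing calendar and the number of patients restarted at EV1.

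For AE rates the conclusion is limited. If person-time starts at the first dose in this study, only restarted patients contribute uncovered time, and the direction of any effect is unknown. What needs correcting there is the unstated starting dose and the absence of a gap-adjusted rate. Severity: should-fix.

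**What to change.** - **SAP 9.0.** Report exposure as the sum over doses of min(days to next dose, 84), with 84 days for the last dose. Keep the present formula, labelled as elapsed time since first risankizumab dose. Where the report refers to about four years of treatment, say which of the two is meant.
- **SAP 11.2.1 item 4.** State that person-time starts at the first risankizumab dose in this study, matching the treatment-emergent rule.
- **SAP 11.2.1, supplementary table.** Keep the treatment-emergent tables as planned. Moving gap events, including malignancies and cardiovascular events, out of the main tables would be a debatable trade-off. Add an AE rate per 100 patient-years that removes events and person-time falling more than the chosen tail after the most recent dose, with the same tail for both, and list the removed events separately.

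The cost is SAP wording, programming from dosing and event dates already collected, one extra table and one extra listing. Reported exposure becomes shorter. The SAP is to be signed before database lock, so the change should be made by then.
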